- b. The number and frequency of nCLE procedure-related AE/SAE from the start of the procedure until end of 12-month follow-up
- 8. To assess the reproducibility of nCLE criteria to the reference standard. Three nCLE characteristics for the detection of malignancy were identified during Wijmans et al. study [10]:
 - a. Dark enlarged pleomorphic cells;
 - b. Dark cell clusters consist of overlapping cell structures ('dark clumps') and
 - c. Continuous movement of the cells in one direction ('directional streaming').
- 9. To create an nCLE image atlas for malignant characteristics in PPNs.

3. Study Design

This is a randomized, controlled, interventional, comparative prospective multi-center study. In total, a maximum of 118 consecutive patients with a (suspected) PPN who are referred for a diagnostic bronchoscopic (Robotic-guided TBNA) procedure will be considered for enrollment. The estimated duration of the study is 24 months. Patients will be consecutively recruited and randomly assigned to undergo Robotic-guided TBNA (n=59) or Robotic-nCLE-guided TBNA (n=59).

Only patients in the nCLE arm will receive intravenously administered fluorescein before the start of the Robotic procedure. During the nCLE procedure, an 18G needle enters the targeted tissue, followed by an nCLE AQ-Flex™ 19N Confocal Miniprobe™ (Mauna Kea Technologies, France) through the biopsy needle, to obtain real-time imaging. nCLE imaging will be performed in the PPNs with a total estimated time for research measurements of 10 minutes. nCLE imaging will be performed for each sequential TBNA pass/sampling within the lung nodule lesion and each TBNA path cytopathological result will be correlated with the nCLE sequence acquired for that TBNA pass. TBNA sampling will end when sufficient diagnostic material will be found with ROSE (as assessed by the cytopathologist) or when the physician performing the procedure judges that the number of samplings/passes is adequate. ROSE will be performed by a cytopathologist.

4. Study Population

Population (base)

Patients with a PPN referred for diagnostic bronchoscopic/endosonographic workup tissue sampling based on standard (PET-) CT imaging

Inclusion criteria

To be eligible to participate in this study, a study subject must meet all of the following criteria:

- ≥ 21 years of age
- Suspected PPN
- Nodule size in CT between 8 mm and 30 mm (largest dimension)

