nCLE requires the administration of exogenous fluorescent contrast. Minutes before CLE positioning, the patient will be administered 2.5 mL of 10% fluorescein IV. A repeat dosage of 2.5 ml of 10% fluorescein can be provided after 15-30 minutes to a maximum dosage of 5 ml of 10% fluorescein in total. Patients will be monitored for allergic reactions, including anaphylaxis. Fluorescein Sodium can be used as a contrast agent with Cellvizio® I.V.E system with Confocal Miniprobes™ without change of formulation, mode of action, approved dose, or route of administration. Refer to the indications for using the fluorescein to perform the injection or to chapter 1: "Fluorescein Angiography: Basic Principles and Interpretation" of Ryan et al. book on Optical Imaging Technologies [25].

The target area will then be identified on the ultrasound and/or fluoroscopy monitor and accessed in the usual manner per standard of care. Once the nodule is localized, an 18G needle with the Confocal Miniprobe™ inside will be introduced through the bronchoscope's working channel and advanced into a lung nodule. After the puncture, the AQ-Flex™ 19 N Confocal Miniprobe™ will then be advanced through the needle into the nodule. Imaging will take place, which will be evaluated by the physician performing the procedure. The on-site image interpretation will be recorded. The AQ-Flex™ 19 N Confocal Miniprobe™ will be removed, and tissue will be aspirated at the imaging site from the tip of the needle that is still in place. ROSE will be performed by the cytology team per standard of care. If no lesional tissue is identified, then the robot may be repositioned for additional needle passes. For each needle pass, a separate CLE movie will be recorded. Multiple needle passes and nCLE imaging may occur, specifically if no tumor is identified on ROSE. In the case of re-localization of the needle, nCLE imaging may be repeated before further needle aspirations. Duration will be recorded after each pass. Chest ultrasound or fluoroscopy will be performed to evaluate for pneumothorax.

7. Puncture the identified target lesion with the needle per standard of care and usual procedure (the Confocal Miniprobe™ is pre-loaded but retracted)	8. Maintain the needle as straight as possible and parallel to the working channel of the scope. (to limit the retraction of the probe within the working channel) Twist the locking device and the probe back onto the needle
	

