3. Lidocaine 10ml will be orally administered to provide local throat and tracheal anesthesia.
4. The bronchoscope will be introduced into the trachea.
5. After target localization (lung tumor), a guiding needle (FlexNeedle 18G, Broncus Medical) will be introduced in the working channel of the scope and on the placement of the endoscope within the bronchus in proximity to the target, the needle is introduced through the bronchial wall and into the lung tumor using fluoroscopy and r-EBUS guidance.
6. **(research-purposes) nCLE acquisitions will be obtained (only in patients in the ROBOTIC-nCLE-guided TBNA arm) by fitting the optical fiber into the TBNA needle and introducing it in the target lesions under fluoroscopy control.**
7. After the nCLE data is acquired and the probe is retrieved, cytological samples will be conducted following a standard protocol (ROSE).
8. Steps 6 and 7 will be performed for each pass.
9. The bronchoscope will be retrieved.

On completion of each procedure, the patients will be extubated and transferred to the recovery area. All patients will be monitored until discharge per standard institutional clinical protocol. This includes a chest x-ray post-procedure to determine whether the patient has suffered a pneumothorax. In the case of a pneumothorax, the complication will be treated with the institutional standard of care. The risks associated with the procedure are no different from a routine bronchoscopy and biopsy. There is a small increased risk

that a patient may have an allergic reaction to fluorescein. Again, this complication will be treated with the institutional standard of care.

nCLE analysis

Each nCLE-video will be analyzed in a blinded fashion to evaluate nCLE lung nodule and lymph node characteristics. The results of the nCLE video reviews will be compared to the corresponding cytological or histopathological results.

Three blinded raters will review nCLE videos for image quality, lung lesion detection and CLE characteristics.

Training session for CLE raters

nCLE raters with various backgrounds will be trained in the nCLE lung cancer criteria using powerpoint slides, hand-drawn schematics and a preselected set of training videos that had not been used previously. Training slides with hand-drawn nCLE lung cancer criteria schematics will also be provided.

Intra-procedure Interpretation of nCLE

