Based on investigator self-assessment, the proportion of cases in which the operator can successfully navigate to the lung target with Robotic guidance and Robotic-nCLE guidance will also be recorded and compared for both arms. Using a statistical test (Student T-test), the navigation success will be compared between arms (Robotic-guided TBNA and Robotic-nCLE-guided TBNA).

Navigation time

Total time that the locatable guide/ nCLE Confocal MiniprobeTM is used in the subject during the Robotic-guided TBNA or Robotic-nCLE-guided TBNA procedure. The navigation time medians and standard deviations will be calculated for both arms. Using a statistical test (Student T-test), they will be compared between arms (Robotic-guided TBNA and Robotic-nCLE-guided TBNA).

First- and cumulative-pass diagnostic yields and performance calculations

First-pass diagnostic yield was defined above (see section Sample size calculation for the definition). Two first-pass diagnostic yields will be calculated one for the Robotic-nCLE-guided TBNA arm and a second one for the Robotic-guided TBNA arm. 95% confidence intervals will be calculated, and the p-value to compare diagnostic yield values between the two arms. Sequential cumulative pass diagnostic yields will also be calculated for each arm.

The diagnostic performance of the sequential cumulative ROSE passes and the sequential cumulative nCLE passes for the Robotic-nCLE-guided TBNA arm and of ROSE only for the Robotic guided TBNA will also be assessed at the end of a follow-up period according to their sensitivities, specificities, positive predictive value (PPV), and negative predictive value (NPV). The sensitivity test will measure the ability of sequential cumulative ROSE passes or sequential cumulative nCLE passes to characterize malignant nodule (true positive rate) correctly. In contrast, the specificity test will measure the ability for sequential cumulative ROSE passes or sequential cumulative nCLE passes to correctly characterize benign nodule (true negative rate) using the final/definitive diagnosis as the reference.

Where a = true positive, b = false positive, c = false negative, and d = true negative:

- Sensitivity: Probability that sequential cumulative ROSE passes will be positive when malignancy is present (true positive rate): $= a/(a + c)$

- Specificity: Probability that a sequential cumulative ROSE passes will be negative when malignancy is not present (true negative rate): $= d/(b + d)$

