- PPV: Probability that malignancy is present when sequential cumulative ROSE passes is positive: $= a/(a + b)$
- NPV: Probability that malignancy is not present when sequential cumulative ROSE passes is negative: $= d/(c + d)$

The same calculations will be performed for the different sequential cumulative nCLE passes. Diagnostic performances for both techniques will be compared using the DeLong and DeLong statistical method [26] with the final diagnosis as the reference diagnosis.

Per patient diagnostic yield (cumulative pass diagnostic yield) and performance calculations

Per patient diagnostic yield of each bronchoscopic procedure (Robotic-guided TBNA and Robotic-nCLE-guided TBNA) is defined as the proportion of patients whose procedure will yield a definitive diagnosis out of the total number of patients that have received that procedure. Two diagnostic yields will be calculated: one for the Robotic-guided TBNA arm and one for the Robotic-nCLE-guided TBNA arm. 95% confidence intervals will be calculated, and the p-value to compare diagnostic yield values between arms.

The diagnostic accuracies of a bronchoscopic procedure (Robotic-guided TBNA and Robotic-nCLE-guided TBNA) will be measured at the end of a follow-up period according to their sensitivities and specificities. The sensitivity test will measure the ability of a technique to correctly identify those patients with the disease (true positive rate). In contrast, the specificity test will measure the ability of the technique to correctly identify those patients without the disease (true negative rate). Sensitivity, specificity, positive predictive value (PPV), and negative predictive value (NPV) will be calculated as the accuracy of the Robotic-guided TBNA and that of Robotic-nCLE-guided TBNA diagnosis (based on final pathology results) compared to the definitive diagnosis based on all available procedures and follow-up.

Where a = true positive, b = false positive, c = false negative, and d = true negative:

- Sensitivity: Probability that a Robotic-guided biopsy will be positive when malignancy is present (true positive rate): $= a/(a + c)$
- Specificity: Probability that a Robotic-guided biopsy will be negative when malignancy is not present (true negative rate): $= d/(b + d)$
- PPV: Probability that malignancy is present when a Robotic-guided biopsy is positive: $= a/(a + b)$
- NPV: Probability that malignancy is not present when a Robotic-guided biopsy is negative: $= d/(c + d)$

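### nCLE imaging is required on every needle pass in three places but only permitted after re-localization in another, so the cumulative nCLE-versus-ROSE comparison (secondary objective 5) can rest on unequal numbers of reads

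*Combined protocol and SAP*

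**What the plan says.** **Statements that require imaging on every pass**
- Section 3 (Study Design): "nCLE imaging will be performed for each sequential TBNA pass/sampling within the lung nodule lesion". It adds that "each TBNA path cytopathological result will be correlated with the nCLE sequence acquired for that TBNA pass".
- Section 5 (Steps of standard and study procedures), where step 6 is nCLE acquisition and step 7 is cytological sampling with ROSE: "Steps 6 and 7 will be performed for each pass".
- Section 5 (Steps during the procedure): "For each needle pass, a separate CLE movie will be recorded".

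**Statements that only permit it**, in the same paragraph as the last of these
- On moving the needle to a new position: "In the case of re-localization of the needle, nCLE imaging may be repeated before further needle aspirations".
- On further passes in general, one sentence before that: "Multiple needle passes and nCLE imaging may occur, specifically if no tumor is identified on ROSE".

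**Analysis that uses the reads.** Section 7 (First- and cumulative-pass diagnostic yields and performance calculations) will assess "The diagnostic performance of the sequential cumulative ROSE passes and the sequential cumulative nCLE passes for the Robotic-nCLE-guided TBNA arm" against the final diagnosis. After giving the formulas for ROSE it says: "The same calculations will be performed for the different sequential cumulative nCLE passes". The two techniques are then compared by the DeLong method. Section 7 does not say how nCLE reads from successive passes combine into one result, or what happens to a pass with an aspirate and no video.

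**The concern.** A second pass is taken mainly when the first ROSE was inadequate, because Section 3 ends sampling once ROSE shows enough material or the operator judges the passes sufficient. The permissive sentence therefore applies to the passes where the operator already knows that ROSE has failed. Reads skipped there would not be missing at random.

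Skipping is plausible in practice. Section 3 puts the research measurements at about 10 minutes in total, and Section 5 describes routine aspiration continuing once the probe is out.

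At stake is secondary objective 5. If ROSE has several looks at a nodule and nCLE has one, part of any difference reflects how often each test was applied and not how well it performs. A video that was not recorded cannot be recovered at analysis, and with no rule in Section 7 the handling would be chosen after the data are seen.

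**Working it through.** **1. The plan's own figures.** Section 4 gives 59 per arm for first-pass yields of 70% and 90%, 80% power, two-sided 0.05. With unpooled variance:

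n = (0.7×0.3 + 0.9×0.1) × (1.960 + 0.842)² / 0.20² = 58.87, rounded up to 59 (power 80.1%).

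The figure reproduces. It uses first-pass yield only, so imaging on later passes does not enter it. Section 4's 29 malignant nodules per arm is 59 × 0.5 = 29.5, rounded down. The plan gives no figure for the cumulative nCLE-versus-ROSE comparison, so the rest is illustration.

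**2. Loss of apparent nCLE sensitivity if only pass 1 is imaged.** Assume that any positive read makes the nodule nCLE-positive. Let
- q = share of malignant nodules that get a second pass;
- a = probability that nCLE is positive on pass 1, given that a second pass is needed;
- b = probability that at least one later read would be positive, given a negative nCLE read on pass 1.

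Loss = q × (1 − a) × b, which cannot exceed q.

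Take q = 1 − first-pass yield, a from 0.2 to 0.9 and b from 0.5 to 0.9. All three are assumptions; the documents give no values for a or b.

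| First-pass yield | q | Malignant nodules with a second pass (of 29) | Most the loss can be | Loss over the range of a and b |
|---|---|---|---|---|
| 90% | 10% | 2.9 | 10 points | 0.5 to 7.2 points |
| 80% | 20% | 5.8 | 20 points | 1.0 to 14.4 points |
| 70% | 30% | 8.7 | 30 points | 1.5 to 21.6 points |

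Example at 90%: 0.10 × (1 − 0.2) × 0.9 = 7.2 points; 0.10 × (1 − 0.9) × 0.5 = 0.5 points.

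**3. Effect on specificity under the same rule.** With independent reads and a per-read specificity of 0.95 (assumption), cumulative specificity is 0.95 for one read, 0.95³ = 0.857 for three and 0.95⁵ = 0.774 for five. Fewer reads therefore make nCLE look more specific while making it look less sensitive.

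**4. How much of a gap to ROSE comes from unimaged passes.** Suppose each technique detects 70% of cancers per pass, reads are independent, there are up to three passes, and sampling stops at a positive ROSE.
- ROSE: 1 − 0.3³ = 97.3%.
- nCLE on pass 1 only: 70.0%.
- nCLE on every pass taken: the probability of no positive read is 0.7×0.3 + 0.3×0.7×0.3² + 0.3²×0.3³ = 0.2100 + 0.0189 + 0.0024 = 0.2313, so sensitivity is 76.9%.

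Of the 27.3-point gap, unimaged passes account for 76.9 − 70.0 = 6.9 points. The other 20.4 points arise because ROSE decides when sampling stops. At 60% per pass the split is 11.1 of 33.6 points; at 80% it is 3.3 of 19.2.

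**The case against.** The strongest reply is that the protocol requires a video on every pass three times, once in the very paragraph that contains the permissive sentence, and links each pass's cytology to that pass's video. On this view one nCLE read against several ROSE reads would be a protocol deviation, and the *may* is only loose drafting. That is fair as a reading of intent. It does not remove the problem, because the permissive sentence stands in the operating instructions and Section 7 is silent on a missing video whatever its cause.

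Three stronger readings are tempting and the documents do not support them.

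- A reader might set 97% for three ROSE passes against 70% for one nCLE read and infer a 27-point bias that vanishes with full imaging. Step 4 shows that, with independent reads, most of that gap remains when every pass is imaged. It would vanish only if the two techniques agreed on every pass, which the plan nowhere claims.
- A reader might infer that nCLE is necessarily disadvantaged. That needs the any-positive rule, which is not stated, and the same rule raises apparent specificity. The DeLong comparison has no predictable direction.
- A reader might extend the point to objective 6, which sets a target per puncture, and want each unimaged puncture scored as inadequate. Section 7 defines imaging feasibility per patient, so an unimaged later puncture does not in itself enter that figure. Such scoring would also merge operator choice with technical failure.

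**Conclusion.** The conflict in wording is real, and Section 7 leaves its consequence unhandled. If operators follow the permissive sentence, the cumulative nCLE-versus-ROSE comparison can rest on unequal reads, with the missing ones chosen by someone who knows the ROSE result.

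The effect is confined to patients with two or more passes and to secondary objective 5. Apparent nCLE sensitivity could fall by at most 10 points at the planned 90% first-pass yield, about 3 of 29 malignant nodules, and by at most 30 points, about 9 of 29, if the yield were 70%. These caps assume that the share of malignant nodules needing a second pass equals one minus the first-pass yield; if operators often take further passes after a diagnostic first one, the share and the cap would be larger. Both figures also assume an any-positive rule and no imaging after pass 1. Because specificity would move the other way, the net effect on accuracy is of unknown sign.

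First-pass yield and the sample size are untouched. This is a correction that should be made, not a threat to the trial's main conclusion.

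**What to change.** - **Section 5 (Steps during the procedure):** reconcile the two permissive sentences with the statements in Sections 3 and 5 that require imaging on every pass. Which imaging rule applies is for the sponsor to decide; the text should say one thing.
- **Section 7:** state how nCLE reads combine across passes, for example whether any positive read makes the nodule positive.
- **Section 7:** state that the paired comparison at cumulative pass k uses the same passes for both techniques, namely those with both a video and an aspirate.
- **Section 7:** report the number of unimaged passes, with the reason for each.

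The cost is a wording change and a few sentences. The paired comparison may use fewer passes. Matching passes equalizes the number of reads, but it removes neither the operator's knowledge of ROSE when deciding to image nor the dependence of stopping on ROSE. The reported reasons are what let a reader judge the first of these.

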2. First-two-passes cumulative diagnostic yield is calculated as the proportion of patients for which first-two-passes cumulative TBNA pass during the bronchoscopic procedure yielded a definitive diagnosis out of the total number of patients that have received a diagnostic procedure.
3. First-three-passes cumulative diagnostic yield is calculated as the proportion of patients for which first-three-passes cumulative TBNA pass during the bronchoscopic procedure yielded a definitive diagnosis out of the total number of patients that have received a diagnostic procedure.
4. Etc.... until the fifth pass.

The number of patients has been calculated to demonstrate an increase of the TBNA first-pass diagnostic yield by 20%, from 70% to 90%, between the Robotic-guided TBNA and the Robotic-nCLE-guided TBNA, with a statistical power of 80% with a 2-sided significance level of 0.05. A group size of 59 patients per arm has been derived. By including 59 patients in each arm, we expect to image at least 29 malignant nodules (prevalence of 0.5) in each arm.

The study will enroll 118 consecutive patients randomly assigned 1:1 to Robotic-guided TBNA arm or Robotic-nCLE-guided TBNA arm.

5. Treatment of Subjects

Investigational product/treatment

In recent years, confocal laser endomicroscopy (CLE) has emerged as a novel technique that enables *in vivo* microscopic analysis during ongoing endoscopy [24]. CLE is based on tissue illumination with a low-power laser with subsequent detection of the fluorescence light reflected from the tissue. It is a contrast-based technique, the most widely used agent being the intravenously administered fluorescein. The probe of the endomicroscopy system consists of a flexible catheter probe representing a bundle of optical fibers linked to a micro-objective, a laser scanning unit, and the control and acquisition software (Cellvizio® I.V.E system, Mauna Kea Technologies, France). The principle of the technique is based on a laser beam of the defined wavelength being focused towards the targeted tissue, and the recaptured signal is displayed as 'optical biopsies' in a single horizontal plane.

[figure not shown]

Figure 1: A- Locking of the CLE probe to the aspiration needle. B- CLE probe inside endosonography needle. C- Endosonography images of n-CLE measurements (white arrow) inside a lymph node (LN) (Wijmans/Annema et al. [10]).

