During the nCLE procedure the bronchoscopist will judge quality of the image, lung lesion detection, and presence of malignancy. The bronchoscopist will be trained in nCLE image evaluation.

Validation session

The trained raters will evaluate nCLE videos of all 59 patients as a randomized data-set and be blinded to the patient history and cytologic/pathologic diagnosis. Videos used for the training session will be excluded. The results of the nCLE video reviews will be compared to the corresponding cytological or histopathological results. The first session will be performed to assess the nCLE characteristics, image quality and confidence and will be used to calculate the inter-observer agreement (IOA) between the raters for detecting malignancies based on nCLE videos. The second session will be performed by the same group of raters, after a 2-week wash-out period, using the same set nCLE videos in a different order to assess the intra-observer reliability (IOR).

Pathological examination

During bronchoscopy, the sites suspected of malignancy will be evaluated with nCLE. In the case of positive tumor cytology (nodes/tumor) or histology (tumor), this will be the reference standard for the nCLE images. In the case of tumor negative cytology or histology, additional surgical/pathological staging or clinical/radiological follow-up will be available.

Cytological aspiration (standard procedure)

During the bronchoscopic procedure, the cytological aspirations will be evaluated on-site by a cytopathologist (ROSE). The appearance of cancer cells will be reported and shown on screen to the endoscopist. Definitive diagnosis of the sample follows after re-evaluation by a staff member of the pathological department. No additional samples will be taken for the research protocol, nor will the research protocol interfere with the pathological diagnostic protocol.

Histological evaluation

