Suppose a patient suspected of lung cancer has a negative result of the bronchoscopic procedure. In that case, a surgical procedure (mediastinoscopy or lobectomy/pneumectomy with lymph node dissection) could follow to obtain tissue. This surgical procedure will be performed regardless of the result of nCLE imaging. If a surgical procedure is indicated, we will collect the histological images to compare with nCLE imaging. This study will not interfere with the standard cytology or the standard histology process. Digital copies of the cytological and histological slides of the measured nodules will be obtained and compared with the frames of the nCLE sequences.

Final Diagnosis or Definitive Diagnosis

For this 12-month analysis, pathology results of Robotic-aided biopsy samples that will be diagnostic of a non-malignant condition or indeterminate will be referred to as negative for malignancy or negative for brevity. Follow-up will be conducted to determine the final diagnosis (malignant or non-malignant). All cases will be followed according to the practitioner's judgment and standard of care testing (e.g., surgical tissue biopsy, repeat Robotic, CT-guided transthoracic needle biopsy or aspiration (TTNA), serial CT imaging, and lung health visits). Cases with subsequent diagnostic tests confirming a non-malignant diagnosis or without lesion progression on radiographic follow-up will be considered true-negative at 12 months, consistent with prior Robotic studies. If the follow-up diagnostics reveal malignancy or lesion growth on repeat imaging with appropriate follow-up diagnostic testing, this will be considered a false-negative. The following will also be regarded as false-negative: death due to lung cancer within 12 months; treatment without a confirmed diagnosis; and new diagnosis of cancer in the lung from any site (including non-index lesions or lymph nodes diagnosed as malignant by linear bronchoscopy during or after the index procedure).

Twelve-month diagnostic yield will be calculated per subject as the rate of true-positives (for malignancy) plus true negatives (for malignancy) of all subjects with attempted lung lesion biopsies.

Adverse Events

Definitions

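### No stated rule lets a positive TBNA become a false positive, so TBNA specificity and PPV will read at or near 100% largely by construction, and the nCLE-versus-ROSE comparison leans towards ROSE

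*Combined protocol and SAP*

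**What the plan says.** All references are to the combined protocol and SAP.

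- Section 5, Pathological examination, sets the reference for nCLE: "In the case of positive tumor cytology (nodes/tumor) or histology (tumor), this will be the reference standard for the nCLE images". For tumor-negative results it relies on further surgical or pathological staging, or on clinical and radiological follow-up.
- Section 5, Cytological aspiration, makes ROSE provisional: pathology staff re-read the same sample to reach its definitive diagnosis.
- Section 5, Final Diagnosis or Definitive Diagnosis, begins from the negatives: "pathology results of Robotic-aided biopsy samples that will be diagnostic of a non-malignant condition or indeterminate will be referred to as negative for malignancy". It says that all cases are followed, and it states when a case is a true-negative and when it is a false-negative. It does not define a false positive.
- Section 7 nevertheless uses a false-positive cell b in specificity, d/(b + d), and in PPV, a/(a + b), for ROSE, for nCLE and for each arm's TBNA. One definition reads: "Specificity: Probability that a Robotic-guided biopsy will be negative when malignancy is not present (true negative rate". Arm-level performance is "compared to the definitive diagnosis based on all available procedures and follow-up". nCLE and ROSE are compared by the DeLong method against the final diagnosis.
- Section 6 collects 12-month data on any index nodule and has the tumor board record a final diagnosis for every patient in both arms.

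**The concern.** Specificity and PPV are informative only if a positive test can be found wrong. Here a positive result serves as the truth for the nCLE images. For TBNA itself, it forms part of the composite truth, with no statement of what happens when a later result disagrees. Two familiar problems follow. One is incorporation: the test is part of its own reference. The other is differential verification: negatives have explicit 12-month rules and positives have none.

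Two outputs are at stake. Readers could take near-perfect TBNA specificity and PPV in both arms as a finding when it was largely assumed. In secondary objective 5, nCLE is set beside ROSE, and the reference comes partly from the specimen that ROSE reads. A TBNA false positive would be credited to TBNA and to a concordant ROSE, while an nCLE reading that was correctly negative would be scored as a miss.

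**Working it through.** **The plan's own figure.** Section 4, Sample size calculation, seeks an "increase of the TBNA first-pass diagnostic yield by 20%, from 70% to 90" per cent, "with a statistical power of 80% with a 2-sided significance level of 0.05", with patients "randomly assigned 1:1 to Robotic-guided TBNA arm or Robotic-nCLE-guided TBNA arm". The unpooled two-proportion formula gives n = (1.960 + 0.842)² × (0.70×0.30 + 0.90×0.10) / 0.20² = 7.849 × 0.30 / 0.04 = 58.9, so 59. This matches "A group size of 59 patients per arm has been derived". It uses first-pass yields only, so neither specificity nor PPV enters it.

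**Can cell b be filled?** Suppose the Final Diagnosis rules did cover positives. A positive TBNA later confirmed as malignant would then be called a false-negative, and one later shown to be benign a true-negative. The rules make sense only for negatives. Section 7's composite could in principle overturn a positive, but it gives no order of precedence. Section 6 names the tumor board without adjudication criteria. Section 6 also recommends treatment for malignant lesions and lists radiation and systemic therapy among the options, so some positives may never have later tissue.

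**Inputs.** Prevalence 0.5 and 59 patients per arm come from the Sample size calculation. The rest are assumptions:
- True nCLE sensitivity and specificity are 0.90 each. The Summary quotes 90% accuracy in tumors from an earlier endoscopic-ultrasound nCLE study, but does not split it.
- True TBNA sensitivity is 0.90.
- True TBNA specificity c runs from 1.00 to 0.90; the documents give no value.
- nCLE and TBNA errors are independent, and ROSE agrees with the final reading of the sample.

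**Formulas when every positive TBNA is taken as malignant.**
- Share misclassified as malignant: F = 0.5(1 − c). Expected number per arm: 59F.
- Reference-malignant share: M = 0.5 + F.
- Apparent TBNA specificity = 0.5c/(0.5c) = 100%. Apparent PPV = (0.45 + F)/(0.45 + F) = 100%.
- Apparent TBNA sensitivity = (0.45 + F)/M.
- Apparent nCLE sensitivity = (0.45 + 0.10F)/M. Apparent nCLE specificity stays at 90%.

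Example, c = 0.95: F = 0.025 and M = 0.525. TBNA sensitivity is 0.475/0.525 = 90.5%, and nCLE sensitivity is 0.4525/0.525 = 86.2%.

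| True TBNA specificity | True TBNA PPV | False positives per arm | Apparent TBNA specificity and PPV | Apparent sensitivity, TBNA / nCLE | Sensitivity gap (truly 0) | TBNA minus nCLE specificity, true → apparent |
|---|---|---|---|---|---|---|
| 100% | 100% | 0 | 100% | 90.0% / 90.0% | 0 | +10 → +10 |
| 99% | 98.9% | 0.30 | 100% | 90.1% / 89.2% | 0.9 | +9 → +10 |
| 97% | 96.8% | 0.89 | 100% | 90.3% / 87.7% | 2.6 | +7 → +10 |
| 95% | 94.7% | 1.48 | 100% | 90.5% / 86.2% | 4.3 | +5 → +10 |
| 90% | 90.0% | 2.95 | 100% | 90.9% / 82.7% | 8.2 | 0 → +10 |

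**Partial verification.** If half the positives were independently verified at c = 0.95, specificity would read 0.475/(0.475 + 0.0125) = 97.4%. PPV would read (0.45 + 0.0125)/0.475 = 97.4%. The inflation shrinks as verification rises.

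**Other TBNA sensitivity.** At true TBNA sensitivity 0.70, the true sensitivity gap of −20 points reads −18.9 at c = 0.99 and −10.0 at c = 0.90. That is a shift of 1.1 to 10.0 points in TBNA's favour.

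**The case against.** The strongest reply is that the plan already looks beyond the index TBNA. All cases are followed, 12-month data cover any index nodule, and the tumor board records a final diagnosis for every patient. The self-reference sentence concerns the nCLE images; for TBNA, Section 7 names a broader composite and keeps cell b. The Sample size calculation counts a TBNA as successful only if it agrees with the final diagnosis, and Section 6 compares intermediate with definitive diagnoses. Both presuppose that they can differ.

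Much of this stands, and it rules out several stronger readings that a reader might infer:

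- *Only negatives are followed.* The documents contradict this. What is confined to negatives is the set of outcome rules.
- *TBNA specificity and PPV are 100% by definition.* That follows only if the nCLE reference rule is also applied to TBNA. Under the composite it is the likely result of a missing rule. Figure 3 was not available to me, so a rule shown only there cannot be excluded.
- *ROSE values are fixed too.* They are not. ROSE can fall below 100% through the re-read of the same sample or a later override.
- *Any nCLE specificity below 100% is an artefact.* The artefact is 100% minus the true TBNA specificity. In the first row of the table the whole 10-point gap is real.
- *Comparing on sensitivity alone avoids the problem.* It does not. Under these assumptions the rule leaves nCLE specificity unbiased and lowers nCLE sensitivity.

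The reply does not supply a rule for discordant results, and the composite still contains the index TBNA.

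**Conclusion.** The concern holds as a gap in the reference standard. With no stated route to a false positive, final-pathology TBNA specificity and PPV will read at or near 100% in both arms largely by construction, and the nCLE-versus-ROSE comparison leans towards ROSE.

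Over an assumed true TBNA specificity of 0.99 to 0.90, TBNA specificity is inflated by 1 to 10 points and a true zero difference in sensitivity appears as 0.9 to 8.2 points against nCLE. These are illustrations, because the documents give no TBNA false-positive rate. The bias is small if that rate is low and absent if it is zero. It would also be smaller if positives were partly verified, or if nCLE and TBNA tended to err on the same nodules.

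The point affects secondary objective 5 and the arm-level performance measures. It should be corrected, but it leaves the primary endpoint's sample size untouched.

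**What to change.** In Sections 5 and 7:

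1. Reconcile the Pathological examination text, the Final Diagnosis text and the definitive diagnosis in Section 7, so that one reference standard serves both TBNA and nCLE.
2. Add a false-positive rule: resection histology or other later tissue, where already obtained, overrides a positive TBNA or ROSE for both references.
3. State that TBNA specificity and PPV are assumed rather than estimated where positives are not independently verified. Do not interpret them as a contrast between arms or against nCLE.
4. Report nCLE and ROSE sensitivity, specificity and PPV also in the subset with an independent reference, noting that it is smaller and selected.

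The cost is wording and one additional table. Surgical histology and 12-month procedures and diagnoses are already collected, so no added procedure or change in care is involved. The downsides are that positives treated without later tissue remain unverified, that subset estimates will be imprecise, and that two measures lose their use as contrasts.
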